6.1.4 Informed Consent Process or Assent (for a minor)

N/A

6.2 Baseline Data Collection

Once consent is obtained, baseline data regarding participant characteristics, injury characteristics, fracture classification, medical history/co-morbidities and The Adherence Estimator,^{33,34} a brief questionnaire assessing the patient's view of prescription medication use will be collected and entered into the METRC custom version of the REDCap data collection system. Characteristics about hospital course and treatment received will also be collected. A brief interview will be conducted with the participant or his/her surrogate.

6.2.1 Medical Record Review

For all enrolled participants, data related to the index hospitalization will be collected. This will include a daily check of the medication administration record to ensure that the patient is receiving the study drug to which he/she was assigned and to document adherence. If treatment is stopped, held or changed the research team member will either identify the reason for change from the chart or by asking the primary team if the reason is not documented. Other data to be collected includes orthopaedic and other injury characteristics, admission labs, and complications, including a fatal bleed, ≥ 2 g/dL drop in hemoglobin, reoperation for hematoma evacuation or surgical site infection, other clinically significant bleeding or infectious complication, VTE, PE, and any imaging studies (and results) conducted for bleeding or VTE concerns. Information on the administration of a limited number of concomitant medications with known potential for bleeding side effects will also be collected, including Plavix, or other platelet inhibitors, aspirin, NSAIDs (e.g. toradol, ibuprofen), and any administration of a full dose of anticoagulation medication, as well as the reason, will be recorded.

Due to the potential affects that COVID-19 has on patients, ie increased risk of clotting, COVID-19 status will be recorded if available via medical record review during the index hospitalization and at follow up. Research team member will record whether the patient is experiencing any symptoms related to COVID-19 or has tested positive. Patients who have tested positive during the index hospitalization will be excluded from the study. Patients who test positive between discharge from the index hospitalization and follow up will remain in the study with data collection of COVID-19 status in the case report form. These data will also be retrospectively collected on all patients who have enrolled into the study since January 2020.

6.2.2 Clinical Assessment

No additional clinical assessments will be conducted as part of this study.

6.3.3 Participant Interview

A Randomized Pragmatic Trial Comparing the Complications and Safety of Blood Clot Prevention Medicines Used in Orthopaedic Trauma Patients Version 11.0 6/1/2021 22

The PREVENT CLOT study protocol is the confidential intellectual property of the PREVENT CLOT Principal Investigators, Steering Committee, and the University of Maryland Baltimore and METRC and cannot be used in any form without the expressed permission of the Principal Investigators.

Participants, or their proxies, will complete a brief baseline data, including age, race, history of tobacco, medical history, including history of VTE, peptic ulcer, DM, or cancer, or if they are immunosuppressed, in addition to use of home OCP/estrogen, Plavix, or daily aspirin. The patient will also be asked to assess their views on prescription medication via The Adherence Estimator questionnaire.^{33,34}

6.3 Participant Follow up and Data Collection

6.3.1 Follow-up Visit Schedule

Each participant will receive a weekly check in via phone call, text message, mobile application or email by an automated computerized system, Twilio, which will be administered centrally from the data coordinating center at Johns Hopkins. Each participant will also have the option of mailing in a pre-addressed, pre-stamped post card documenting adherence using provided by the study team (Attachment F). Each week, participants will respond to a series of questions, that contain questions from The Brief Medication Quesitonnaire,³² with automated responses designed to assess adherence to study assigned medication, potential medication crossover and use of other blood clot prophylaxis. At the time of this contact, if a participant is found to no longer be taking prophylaxis for any reason other than discontinuation by the treating physician, the participant will receive a message that he/she is at increased risk of blood clot due to his/her injury experience, and should contact his/her surgeon to determine whether or not continued prophylaxis is still indicated (Attachment B). If the patient does not respond to two subsequent surveys they will be contacted by a representative from the coordinating center. The automated contact will stop when the participant responds that prophylaxis is no longer indicated or at the time of the 3 month follow-up visit, whichever comes first.

Participants may opt out of this contact at the time of enrollment or any time during the follow up period.

All outcomes in this study will be assessed at 90 days (3 months) post randomization, and all efforts will be made to ascertain outcomes at this point in time. Because this is a pragmatic study and there are no study visits, participants will also complete a visit which will coincide with a regularly scheduled standard of care follow-up visit approximately 3 months post randomization at which point study outcomes will be assessed. If participants are unable to return to the clinic they may be contacted to complete the 3 month follow up visit via phone call, email, or mail. If a patient completes the follow up visit prior to the 3 month anniversary, a medical record review will be conducted in order to assess for potential outcomes that were not recorded at the premature follow up visit. To fully assess for any missed outcomes, the research coordinator may assess for potential events in the patient's medical record..

At the time of the 3 month follow up visit (in-person or virtual), participants will be interviewed by the Research Coordinator to assess for the occurrence of any clinical outcomes, including VTE events or complications secondary to treatment since their hospitalization. For each event identified, the participant will fill out a release of information form that will allow the research staff to obtain records related to the event, if they occurred outside the index facility. Participants A Randomized Pragmatic Trial Comparing the Complications and Safety of Blood Clot Prevention Medicines Used in Orthopaedic Trauma Patients Version 11.0 6/1/2021 23

The PREVENT CLOT study protocol is the confidential intellectual property of the PREVENT CLOT Principal Investigators, Steering Committee, and the University of Maryland Baltimore and METRC and cannot be used in any form without the expressed permission of the Principal Investigators.

will be asked about study medication satisfaction using the Treatment Satisfaction Questionnaire for Medication (TSQM)³¹ and about their total out of pockets costs related to obtaining the study assigned medication. Additionally, the medical record will be carefully reviewed to assess for any complications treated at the index facility, including in the clinic, ED, or resulting in a rehospitalization.

As stated above, due to the potential affects that COVID-19 has on patients, ie increased risk of clotting, COVID-19 status will be recorded if available via medical record review also at follow up. Research team member will record whether the patient is experiencing any symptoms related to COVID-19 or has tested positive. This data will be collected on all patients who have enrolled into the study since January 2020.

Lost to follow up participants

A percentage of participants will fall in the category where they cannot be contacted, do not return to clinic, or return to clinic but do not have 90 days of follow-up. Additional contact methods will be used to verify these participants' death status which is critical for determining the primary outcome, all-cause mortality. The following methods, which are also described in more detail below, will be used to assess outcomes on these individuals: (1) medical record review, (2) postcard questionnaire, (3) phone call or text follow up from coordinator (4) search via LexisNexis Accurint system, (5) phone call and text message follow up from MCC, (6) search via Limited Access Death Master File (LADMF)

Medical Record Review

If the participant cannot be contacted and does not return for a final research visit, medical records will be abstracted through the last orthopaedic encounter occurring between anytime from the last clinical encounter to the time of medical record review. The visit occurring closest to the 3 month follow-up target should be recorded(e.g. for a participant seen at 60 days, 185 days and 400 days, the 60 day visit should be recorded to demonstrate use of services in the follow-up interval, and the 185 day visit should be recorded to demonstrate that the participant was alive and free of any orthopaedic events at 185 days and therefore also alive and event-free at 90 days, the date of interest. No other visit data should be recorded. Attempts will be made to obtain medical records or autopsy reports for all participants who are discovered to be deceased at the time of the follow up visit. If the participant died at home, family members will be asked to provide a cause of death, if known. No attempts will be made to follow up with family, and the deaths will be recorded as "unknown" cause.

If a patient cannot be contacted AND has no evidence of returning for any orthopaedic clinical visit, the medical record will be searched for any evidence of an encounter with the medical system documenting that the patient survived through at least 3 months post randomization. If the encounter occurred before 3 month post randomization information, information related to study outcomes available at the encounter. If the encounter occurs anytime following the 3 month post randomization date the date and visit type will be recorded. The resulting information

The PREVENT CLOT study protocol is the confidential intellectual property of the PREVENT CLOT Principal Investigators, Steering Committee, and the University of Maryland Baltimore and METRC and cannot be used in any form without the expressed permission of the Principal Investigators.

will provide evidence that the patient was alive during the window of interest, allowing ascertainment of information on the primary outcome.

Postcard questionnaire

Each lost to follow up participant will receive a one-time pre-stamped postcard questionnaire requesting information on the participant's death status. The postcard will be addressed to the participant however may be returned by a family member, friend, or resident of the participant's home. Sample of this postcard is in Attachment H.

To facilitate centralized distribution and retrieval of these cards, clinical sites will send the patient's full name and mailing address, along with the study ID number, to the MCC using a secure, encrypted, password-protected File Transfer Protocol. The MCC will centrally send out postcards using an automated postcard development and mailing electronic service.

Phone call/text message follow up (Research Coordinator)

Research coordinators will call the participant or emergency contact listed in the participant's medical record or social work/case management file to determine the participant's death status. This phone call will be in addition to any attempts made during the follow up period. If the Research Coordinator gets in contact with the patient a full follow up visit and questionnaire will be conducted. If the Research Coordinator can only determine the participant's death status based on conversations with the family and/or emergency contact the death status will be recorded. Sample of the text message/call script is in Attachment I.

Search via LexisNexis Accurint Services

The MCC will obtain identifiers such as but not limited to the patient's name, date of birth, social security number, and last known address using a secure, encrypted, password-protected File Transfer Protocol. The identifier will be used to conduct probabilistic mapping through public and proprietary database search. Any identifiers will aid in specialized mapping of this database will be used in the search, and the database will return up to date mailing and phone contact information for the participant, as well as any publicly reported deaths.

Phone call/text message follow up (Centralized through MCC)

The MCC will centrally contact each participant and emergency contact, when necessary to evaluate the death status of the participant using the contact phone numbers previously provided by participating centers for weekly follow up as well as information obtained from the Accurint search. Clinical sites may also obtain any additional phone numbers associated with the participant's medical record and transfer it, along with the study ID number, to the MCC using a secure, encrypted, password-protected File Transfer Protocol. All statues will be saved in REDCap. Sample of the text message/call script is in Attachment I.

Search via Limited Access Death Master File (LADMF)

The PREVENT CLOT study protocol is the confidential intellectual property of the PREVENT CLOT Principal Investigators, Steering Committee, and the University of Maryland Baltimore and METRC and cannot be used in any form without the expressed permission of the Principal Investigators.

There will be a subset of patients who cannot be contacted AND have no evidence of any further encounters with the clinical system. For these cases, ascertaining final death status is critical to the validity of the study, and the study team has developed a plan to allow sites to obtain this information while conforming to local policies regarding the sharing of PHI and accessing available data. Because this study is being executed in 21 trauma centers, including 2 centers in Canada, the method for determining if a patient passed away during the study interval will vary. Local IRBs will review the protocol and make a determination regarding if and how this information will be obtained, according to the following options:

- A. Sites have the option to send a secure, encrypted password-protected LOOK-UP File to the MCC for a centralized database search of the Limited Access Death Master File (LADMF).
- B. Sites have the option to locally and independently access the LADMF or local death record database, including Canadian sites, to conduct a search of patients.
- C. Sites are unable to access the LADMF either locally or send data for a centralized search and therefore opt out of obtaining this information for their patients.

Option A: Established by the National Center for Health Statistics of the Centers for Disease Control and Prevention (CDC) the LADMF is a centralized database of death record information of all state vital statistics offices. The LADMF requires at least one of the following identifiers: name, date of birth, and social security number to obtain accurate information. Consequently, for each patient completely lost to follow up, clinical sites may obtain the patient's social security number from the hospital billing record and transfer it, along with the study ID number, patient name, and date of birth to the MCC using a secure, encrypted, password-protected File Transfer Protocol. The MCC will link these data with the Social Security Administration Death Master File to determine if a death has been registered for the study patient. Only the study ID and death status for the patient will then be linked to the study database.

A HIPAA waiver will be sought to cover the exchange of PHI between institutions for patients whose death status is unknown to determine the primary outcome on patients who are lost to follow up. The data obtained for this purpose will be saved in a separate LOOK-UP file and will not be linked to contact data or identifiable data of the study dataset.

The MCC may access the patient's SSN and develop a LOOK-UP File for all those individuals identified as loss to follow up with unknown death status. This LOOK-UP File contains information needed to conduct a search on the LADMF (may include: name, date of birth, SSN). A HIPAA waiver will be sought to share this information for the purposes of obtaining death status on every patient who is lost to follow up with no indication of the status of this outcome.

Waiver of Consent. We are requesting a waiver of consent for accessing identifiable data. We believe that we meet the Code of Federal Regulations criteria for a waiver of consent as follows:

Can informed consent be waived or consent elements be altered under 45 CFR 46.116(d)

The PREVENT CLOT study protocol is the confidential intellectual property of the PREVENT CLOT Principal Investigators, Steering Committee, and the University of Maryland Baltimore and METRC and cannot be used in any form without the expressed permission of the Principal Investigators.

- a. The research involves minimum risk to subjects:** Yes, the research will involve existing data
- b. The waiver or alteration will not adversely affect the rights and welfare of the participants:** Yes, the data currently exist and will only be used for the search and determination of status. The analysis will be conducted using de-identified data with additional data will be collected, nor will any procedures be performed as part of the proposed analysis.
- c. The research could not practicably be carried out without the alteration or waiver:** Yes. The cases where the patient is lost to follow up would not allow for an opportunity to obtain consent.
- d. Whenever appropriate, the subject will be given additional information about the research after it is completed:** Yes. Study results will be posted on a study website.

Option B: For sites that will conduct a search locally will obtain an account to and search the LADMF or a different local death record database independent of the MCC. The results of each patient's primary outcome status will be recorded in the patient case report form. Sites are permitted to use a local death record centralized databased in addition to or instead of the LADMF to obtain final death status on lost to follow up patients.

Option C: For sites that will not conduct a search either locally or centrally through the MCC will not obtain the primary outcome on these patients and those data will be considered missing.

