3. the number of patients not enrolled and associated reasons
4. the number of enrolled and randomized patients
5. number randomized to aspirin group, number randomized to low-molecular-weight heparin (LMWH) group
6. within treatment group, the number of late ineligibles, late refusals, and inappropriate enrollments
7. within treatment group, the number initiating treatment protocol
8. within treatment group, information on 90 day follow-up (including separate metrics for key endpoints)
9. within treatment group, the number included in the per-protocol analysis

The independent adjudication committee will make the final determination on late ineligibles and inappropriate enrollments while masked to the treatment arm. Late ineligibles and inappropriate enrollments will be removed from all analyses. The outcomes, complications, adverse events of late ineligibles and inappropriate enrollments who received treatment will be reported, to the extent possible.

3 Follow-up Time

Patients were expected to return for a study follow-up visit at 90 days post admission. If participants are unable to return to the clinic, they may be contacted to complete the 90 days follow up visit via phone or email. In addition, medical record reviews will be conducted to determine whether there was documented clinical/research contact beyond the last study follow-up visit. If that visit occurred less than 90 days following randomization, the end of follow up will be defined as the last study follow-up visit or the last clinical/research contact if applicable, and follow-up time will be the duration between randomization and the end of follow up. A figure showing the distribution of follow-up time through 90 days by treatment group will be produced. Differences between treatment groups based on follow-up time through 90 days will be evaluated. Details of reasons for premature study discontinuation will be presented.

4 Baseline Characteristics

A table will report summary statistics of baseline characteristics of participants by treatment groups. Characteristics will include age, sex, body mass index, tobacco use, history of venous thromboembolism, co-morbidities, additional medications, health insurance status, injury severity score, and injury region.

5 Adherence to Treatment Protocol

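### A visit after day 90 proves survival to day 90, but section 6.3.1 and SAP section 3 also let it count as complete, event-free follow-up for the non-fatal outcomes

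*Combined protocol and SAP*

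**What the plan says.** The relevant text is in Protocol Version 11.0, section 6.3.1, and SAP sections 3 and 7.

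- **Patients who are reached.** At the 3-month visit, "participants will be interviewed by the Research Coordinator to assess for the occurrence of any clinical outcomes". Events treated outside the index facility are traced with the patient's help: "For each event identified, the participant will fill out a release of information form".
- **Patients who are not reached but have orthopaedic visits.** The Medical Record Review paragraph opens "If the participant cannot be contacted and does not return for a final research visit", and for these patients "medical records will be abstracted through the last orthopaedic encounter". Its worked example has visits at days 60, 185 and 400. Days 60 and 185 are logged, and the day-185 visit is taken to show the patient was "alive and free of any orthopaedic events at 185 days and therefore also alive and event-free at 90 days". The example ends "No other visit data should be recorded".
- **Patients who are not reached and have no orthopaedic visit.** Any later contact with the medical system is sought: "If the encounter occurs anytime following the 3 month post randomization date the date and visit type will be recorded". The protocol presents this as evidence of survival, for the primary outcome.
- **SAP section 3.** If the last visit fell before day 90, "the end of follow up will be defined as the last study follow-up visit or the last clinical/research contact if applicable". No distinction is made between death and other outcomes.
- **SAP section 7.** Patients lost to follow-up are treated as still at risk. Estimands 2 to 9 are risk differences for events being observed by day 90, had nobody been lost. They receive 95% confidence intervals and no hypothesis tests.

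**The concern.** Survival runs backwards in time: a patient alive at day 185 was alive at day 90. Freedom from a PE, DVT, bleed, wound complication or infection does not. Such an event can occur at day 40, be treated at another hospital, and have resolved by a clinic visit months later. Section 6.3.1 nevertheless carries event-free status back along with survival.

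The SAP then gives the inference analytic force. With one end-of-follow-up date for all outcomes, a contact after day 90 gives the patient full 90-day follow-up in the cumulative incidence estimates for Estimands 5 to 9. An uncharted event is therefore counted as a non-event instead of being handled by censoring. On the SAP's wording, even an encounter that yields only a date and a visit type would do this.

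At stake is the accuracy of the secondary efficacy and safety differences, which are the evidence on Aims 2 and 3. Patients classified this way also no longer appear as missing, so the missing-data sensitivity analyses in protocol section 10.3 would not reach them.

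**Working it through.** **Plan's own figures.** The documents give no figure for this bias. Two nearby power statements reproduce.

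- Primary outcome (section 10.1: 1.0% in both arms, margin 0.75%; upper bound of a two-sided 96.2% interval, so one-sided 0.019). With 6,100 × 0.925 ≈ 5,642 per arm, SE = √(2 × 0.01 × 0.99 / 5,642) = 0.187 points. Power = Φ(0.75/0.187 − 2.075) = 97.3%, consistent with the stated figure of more than 95%. The rule does not affect it.
- Version 1.0 Aim 3 (10% v 8.47%): 80.2% power at 5,642 per arm, against 80% stated. These rates are superseded and serve below only as illustration.

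**What each route shows**

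| Route | Information obtained | Supports survival to day 90 | Supports no non-fatal event to day 90 |
|---|---|---|---|
| Reached | Interview, outside records by release, chart | Yes | Yes |
| Not reached, later orthopaedic visit | Chart abstraction | Yes | Only for charted events |
| Not reached, other later encounter | Date and visit type | Yes | No |

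On its wording, SAP section 3 gives all three the same 90-day follow-up.

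**Formula.** Let *a* be the share of patients classified from a later visit, *m* the share of their events absent from the chart, and *f = a × m*. Assume these patients have the same event risk as the rest. The observed risk is p(1 − f), so the observed difference is

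RD_obs = p_A(1 − f_A) − p_L(1 − f_L),

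which is RD × (1 − f) when f is equal in the two arms.

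**Equal arms.** Take a = 7.5%, the only attrition figure in the documents, as if every lost patient were classified this way.

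| m (assumed) | f | Shift on 1.53 points (bleeding/infection) | Shift on 0.87 points (PE) |
|---|---|---|---|
| 20% | 1.5% | 0.02 | 0.01 |
| 50% | 3.75% | 0.06 | 0.03 |
| 100% | 7.5% | 0.115 | 0.065 |

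The 1.53 is 10% − 8.47%. The PE case takes 1.5% on LMWH from Version 1.0 and assumes 2.37% on aspirin. For scale, at 6,100 per arm the 95% half-widths are:

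- bleeding/infection: 1.96 × √(0.10 × 0.90/6,100 + 0.0847 × 0.9153/6,100) = 1.03 points;
- PE at 1.5% in both arms: 1.96 × √(2 × 0.015 × 0.985/6,100) = 0.43 points.

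With a constant hazard and only day 60 to 90 events missed in 7.5% of patients, −1.53 becomes −1.49. With day 5 to 90 events missed it becomes −1.42.

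**Unequal arms.** Assume f of 10% in one arm and 5% in the other. These average to the 7.5% ceiling, so this is an extreme case.

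- Aspirin 10%, LMWH 5%: 8.47 × 0.90 − 10 × 0.95 = −1.88, away from zero.
- Aspirin 5%, LMWH 10%: 8.47 × 0.95 − 10 × 0.90 = −0.95, toward zero.
- PE, aspirin 5%, LMWH 10%: 2.37 × 0.95 − 1.5 × 0.90 = +0.90, away from the true +0.87.
- No true difference at a 10% event rate: 10 × (0.95 − 0.90) = 0.50 points, in either direction. If only half of these patients' events were uncharted, the figure is 0.25 points.

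**The case against.** The case for leaving the text alone has several parts.

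- *The chart is read first.* Abstraction through the last orthopaedic encounter is required, and section 10.3 also tells sites to fill gaps from records. This stands: only uncharted events are lost. A reader might infer that all missing PE, DVT and bleeding data become non-events, but the documents do not support that.
- *The sentence concerns orthopaedic events.* It does not name PE, DVT or bleeding, and the subsection is mainly about death status. This stands in part. The scope is undefined, and the SAP's single date applies the result to every outcome whichever meaning was intended.
- *The bar on other visit data only says which visits to log.* That is a fair reading, since it closes an example and complications have their own items in the Appendix B schedule. A coordinator could still take it as a reason not to record an intervening encounter.
- *Records are the main source for everyone.* SAP section 7.1 puts standard care and record review first, so missing outside events is partly a feature of this pragmatic design. Even so, patients who are reached also have the interview and the release form.
- *The estimands concern observed events.* They are also defined as if nobody were lost, and in that setting these patients would have had the planned interview.
- *Follow-up is reported by arm, with separate metrics for key endpoints.* This is useful, but it is reporting and does not change who is censored.

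**Conclusion.** The rule is right for death and wrong, as written, for Estimands 5 to 9. The primary outcome, its power and every formal test are untouched.

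The size is modest: a relative under-count of 1.5 to 3.75%, and at most 7.5%, at planned attrition. This assumes that all lost patients are classified this way, that 20 to 50% of their events are uncharted, and that their event risk matches that of other patients. Fewer reclassified patients would scale it down in proportion. Larger shares of patients, such as 15%, would be twice the attrition the documents plan for. The equal-arm shifts are small against the interval widths.

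Two stronger readings are tempting. One is that the rule always pulls differences toward zero. That needs equal missed-event fractions in both arms, which nothing in this open-label trial establishes; unequal fractions can move the difference either way or create one. The other is that the rule tilts a non-inferiority decision on Aim 2 or a superiority decision on Aim 3. Version 11.0 runs no such tests and sets no margin for Aim 2, so the effect is on how the intervals are read.

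The change is still worth making. The stated inference is invalid, it bears on the efficacy and safety secondaries, and the correction is cheap.

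**What to change.** 1. In section 6.3.1, let a contact after day 90 establish vital status only, unless a record review covering all of days 0 to 90 for the non-fatal outcomes was done. State what orthopaedic events means.
2. In SAP section 3, keep the present date for death and define a separate one for Estimands 5 to 9: the last date through which those outcomes were ascertained by interview or by such a review, capped at day 90. Set it by the same rule whether or not an event was found. Otherwise a charted day-75 event would count while a matching event-free patient was censored at day 60, which biases incidence upward.
3. Replace the bar on recording other visits with an instruction to record any encounter in days 0 to 90 that shows a study outcome.
4. Report by arm how many patients were classified from a visit after day 90. Add a sensitivity analysis that censors them at their last direct ascertainment.

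The cost is wording in two places, a second censoring date, slightly more censoring, and slightly wider intervals on the secondary outcomes. Events treated elsewhere can still escape a full review of the index chart; the sensitivity analysis in item 4 shows how much the results depend on these patients.
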